^a **Rationale:** The original label for EPO²⁹⁻³⁰ included a warning regarding the risk of exacerbation of hypertension with hematocrit increases exceeding 4 percentage points (corresponding to increases in the hemoglobin concentration of approximately 1.3 g per deciliter) within a 2-week period. During a review of the marketing application, an association was found between rates of increase in the hemoglobin level exceeding 1g/dL per 2-week period and the risk of cardiovascular and thromboembolic events. This observation provided the basis for a warning on the package insert for darbepoetin regarding excessive rates of increase in hemoglobin concentrations.

Continuation of Dosing of EPO (Post-Operative Administration)

Postoperative therapy will **NOT** be administered in patients under the following conditions:

- Hb concentration $>10.0\text{g/dL}$ (both CABG and valve procedures)^b
- Rotational Thromboelastogram (RoTEM) measurement of Maximum Clot Firmness (MCF) $>70\text{mm}$ (RoTEM to be performed during procedure and 2-4 days after surgery, prior to re-dosing).
- Evidence of any new or evolving symptoms or signs suggesting the presence of myocardial ischemia, including chest pain, EKG changes, or elevation of laboratory cardiac biomarkers (CK-MB, Troponin) that have failed to have a decreasing trend
- Average of three diastolic blood pressures (over 1hr) $>100\text{mmHg}$ despite scheduled anti-hypertensive therapy.

^b **Rationale:** A multi-center study in over 2,000 CABG patients by Spiess et al.¹² demonstrated that hematocrit $>34\%$ (11.3g/dL) upon entry in the ICU was the single greatest predictor of myocardial infarction following surgery. Furthermore, according to the labeling for EPO targeting higher hemoglobin (13 to 14g/dL) compared to a lower range (9 to 11.3g/dL) increased the risk of death, myocardial infarction, stroke, and thrombotic events in patients *with CKD*.²⁹⁻³⁰

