- Patients in the treatment group will be seen again in a Patient Blood Management infusion room to receive a single subcutaneous injection of EPO 300U/kg and a 2nd IV iron infusion of 510mg, if iron reserves are believed to be inadequate (for a major hemorrhage) based on the result from the baseline iron panel and per Surveillance Strategy guidelines.

- Vitals signs, including heart rate, blood pressure, oxygen saturation, and temperature will be recorded before, during, and after drug administration.
- Patient will be monitored for any serious reactions (anaphylaxis, chest pain, dyspnea, seizures, severe headache, fever, nausea, vomiting, and diarrhea, an increase in blood pressure greater than 20mmHg above baseline systolic, systolic BP greater than 180mmHg and/or diastolic BP greater than 100mmHg, hypotension).
- Approximately 8mLs of blood will be drawn to obtain troponinT/CK-MB and reticulocyte count.
- The visit will last approximately 1 hour.

Day of Surgery

- We will monitor the patient's vitals (blood pressure, EKG, etc) as part of standard care.
- Approximately 8mLs of blood will be drawn to obtain hemoglobin concentration and reticulocyte count.

Post-Operative Dose

- Approximately 3mLs of blood will be drawn for a rotational thromboelastogram (RoTEM) measurement prior to redosing.
- Patients in the treatment group will receive a single subcutaneous injection of EPO 300U/kg two to four days following surgery, if they meet criteria as described in the surveillance plan.
- Vitals signs, including heart rate, blood pressure, oxygen saturation, and temperature will be recorded before and after injection.
- Patient will be monitored for any serious reactions (chest pain, dyspnea, seizures, severe headache, fever, nausea, vomiting, and diarrhea, an increase in blood pressure greater than 20mmHg above baseline systolic, systolic BP greater than 180mmHg and/or diastolic BP greater than 100mmHg).

Post-Operative Days #5, #7, #14

- On Day #5 approximately 8mLs of blood will be drawn to obtain a reticulocyte count, iron panel, AST/ALT.
- On Day #7 approximately 8mLs of blood will be drawn to obtain a reticulocyte count, CBC and creatinine (unless done as SOC).
- On Day #14 or at discharge approximately 6mLs of blood will be drawn to obtain a CBC and creatinine (unless done as SOC).

Clinical Outcomes

The primary objective is to assess the enrollment rate and adherence to the dosing protocol and

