The cost of erythrocyte transfusions, EPO plus iron, direct hospital costs and direct margins associated with the care of those randomized in this pilot study will be recorded for future analysis of resource utilization. The duration of operating room time, intensive care unit and hospital length of stay will be collected. The total cost of erythrocyte transfusion will be based on four times the acquisition cost (\$1,200.00)⁴⁷ The cost of EPO and IV iron will be calculated based on recommended manufacturer suggested retail price at the time of publication and will include activity based costs of administering these treatments based on the protocol outlined in this study.

IV. STUDY PROCEDURES:

Time Line of Pilot Study

Note: Supplementation with intravenous iron (feraheme; 510mg delivered as an IV infusion) will only be administered following the first two preoperative doses of EPO (shown in diagram).

Consort Diagram of Pilot Study:

[figure not shown]

Table 1. SUBJECT SCHEDULE OF EVENTS

Test/evaluation & collected/required forms	7-28d PreOp	1-7d PreOp	POD0 PreOp	POD0 PostOp	POD 1	POD 2	POD 5	POD 7	POD 14
Inclusion & exclusion criteria	X								
Informed consent/HIPAA	X								
Demographics	X								
Medical History/Meds	X								
Physical examination	X	X	X	X	X	X	X	X	X
Body mass index	X								
Vital signs	X	X	X	X	X	X	X	X	X
ASA	X								
Laboratory									
CBC	S	S	S	S	S	S	S	S	S/X
Reticulocyte Count	S	X		X	S		X	X	
Iron panel**	S		X		S		X		
Creatinine	S	S	S	S	S	S	S	S	S/X
Troponin T/CK-MB		X		S	S	S/X			
AST/ALT		S			S		X		
Rotational Thromboelastogram (Rotem) ⁺				S		X			
12-lead EKG	S	S	S	S	S	S	S	S	
Record of Erythrocyte transfusion	X	X	X	X	X	X	X	X	X
Estimated blood loss				X	X	X			
Adverse Events	X	X	X	X	X	X	X	X	X
Patient Survey	X								
Protocol Compliance	X	X	X	X	X	X	X	X	X

S = Standard of Care laboratory tests routinely ordered per ICU care team

X = Not routinely ordered laboratory tests; obtained for research purpose only.

*Will obtain hemoglobin and creatinine on POD14 or before hospital discharge (whichever event occurs first)

**Iron panel includes ferritin, TIBC, iron, transferrin

⁺ Will obtain RoTEM EXTEM 2-4 days after surgery

Adverse events and survival will be reviewed at the time of hospital discharge and 30d following surgery.

V. SUBSTUDY PROCEDURES

Our study does not include any sub-studies.

VI. CRITERIA FOR INCLUSION OF SUBJECTS:

The inclusion criteria of subjects are as follows:

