1. The subject must be between the age of 18 and 80 years old.
2. The subject must be diagnosed with preoperative anemia, defined as hemoglobin <13.0g/dL.
3. The subject must be scheduled for elective cardiac surgery (CABG, valve, or CABG/valve), including both first time and repeat procedures.
4. Female subjects of child bearing potential must have a documented negative pregnancy test within 7 days prior to the procedure.

5. The subject must sign a written informed consent prior to the procedure, using a form that is approved by the UT Southwestern Institutional Review Board.
6. The subject must agree to be compliant and return for all follow-up visits.

VII. CRITERIA FOR EXCLUSION OF SUBJECTS:

The subjects will be excluded if they meet any one of the following criteria:

1. Uncontrolled hypertension (defined as systolic pressure greater than 180mmHg, diastolic pressure greater than 100mmHg, not adequately controlled by anti-hypertensive therapy at the time of procedure).
2. Current renal failure on dialysis or serum creatinine [Cr]>3.0mg/dL. ¹
3. Unstable angina (defined by chest pain and ECG changes indicating ischemia at rest).
4. Thromboembolism within the past year.
5. Current active primary or metastatic malignancy or history of myeloid malignancy.
6. Seizures within the past year.
7. History of stroke within the last 6 months.
8. Patients who have platelet count lower than 50,000/mm³ or coagulation abnormality.
9. Sepsis or bacteremia defined by positive blood culture.
10. Patients who have known hypersensitivity to EPO or any of its components.
11. Patients who have known hypersensitivity to Feraheme or any of its components.
12. Patients who refuse blood transfusion, (i.e. Jehovah's Witnesses).
13. Pregnant or breast feeding.
14. Patients who are unable to provide informed consent or who has inability to understand or cooperate with study procedure.

VIII. SOURCES OF RESEARCH MATERIAL

Data will be obtained from the patient's medical records EPIC and the Society of Thoracic Surgery (STS) database entries. Laboratory tests for reticulocyte count and additional serum ferritin, cardiac biomarkers, serum creatinine, thromboelastographic and liver transaminase measurements will be obtained specifically for research purposes. Other tests conducted (e.g. hemoglobin concentration, creatinine, EKG) will be part of standard of care (see Table 1 for details regarding standard of care and for research only).

IX. RECRUITMENT METHODS AND CONSENTING PROCESS

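### Troponin/CK-MB is last scheduled on POD 2, so a postoperative EPO dose on POD 3 or 4 can rest on a marker 1 or 2 days old, although RoTEM for the same hold rule is tied to the dose

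*Combined protocol and SAP*

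**What the plan says.** **Dose window.** Under Post-Operative Dose (Section III), treated patients receive one EPO injection "two to four days following surgery, if they meet criteria as described in the surveillance plan".

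**Hold rule.** Continuation of Dosing of EPO (Section III) gives four grounds for withholding this dose: hemoglobin above 10.0 g/dL, RoTEM maximum clot firmness above 70 mm, evidence of myocardial ischemia, and diastolic pressure averaging above 100 mmHg despite treatment. The ischemia ground covers chest pain, EKG changes, or "elevation of laboratory cardiac biomarkers (CK-MB, Troponin) that have failed to have a decreasing trend".

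**RoTEM timing.** The hold rule states it: "RoTEM to be performed during procedure and 2-4 days after surgery, prior to re-dosing". The dose visit repeats it: "Approximately 3mLs of blood will be drawn for a rotational thromboelastogram (RoTEM) measurement prior to redosing". Table 1 marks RoTEM in the POD 2 column and adds the footnote "Will obtain RoTEM EXTEM 2-4 days after surgery".

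**Marker timing.** The troponin T/CK-MB row of Table 1 has X at 1-7 days before surgery, S on POD 0 after surgery, S on POD 1 and S/X on POD 2. The POD 5, 7 and 14 cells are blank. Table 1 has no POD 3 or POD 4 column for any item, and the marker row carries no window footnote. The dose visit names no marker draw, and the Day 5 draw covers reticulocytes, iron panel and AST/ALT only.

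**The concern.** One hold rule uses two laboratory inputs that both sit in the POD 2 column. One is expressly tied to the dose on whichever day it is given; the other stops at POD 2. Someone following the schedule could give the injection on POD 4 with a RoTEM result obtained for that dose and a troponin from two days before.

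Before surgery the plan handles this differently. The visit at which the second EPO dose is given has its own marker draw: "Approximately 8mLs of blood will be drawn to obtain troponinT/CK-MB and reticulocyte count". Only the postoperative dose lacks a marker attached to it.

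What is at stake is patient safety. Section X acknowledges that EPO is off-label in this setting and may raise cardiovascular risk, including death, and it presents the surveillance strategy as an added protection against thrombotic events. A marker that starts to rise on POD 3 is the kind of signal the hold rule is meant to catch, and no scheduled test would show it before a POD 3 or POD 4 dose.

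**Working it through.** The plan states no figure to reproduce here, and no power or error-rate calculation applies. The check is schedule arithmetic.

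**Inputs**
- Dose days allowed: POD 2, 3, 4 (Section III, Research Design and Methods and Post-Operative Dose).
- Last scheduled troponin/CK-MB: POD 2 (Table 1).
- RoTEM: days 2-4, before re-dosing (Section III and the Table 1 footnote).
- Treated patients: 25 in total, of whom 23 are still to be enrolled (Section III, Research Design and Methods).
- Postoperative doses per patient: at most 1.

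**Age of the latest scheduled marker** = dose day minus POD 2

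| Dose day | Marker age | RoTEM |
|---|---|---|
| POD 2 | 2 - 2 = 0 days | before the dose |
| POD 3 | 3 - 2 = 1 day | before the dose |
| POD 4 | 4 - 2 = 2 days | before the dose |

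Scheduled marker tests after POD 2: 0.

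**What the scheduled values can show.** The criterion is about trend. POD 0, POD 1 and POD 2 give three postoperative values, enough to judge a trend up to POD 2. They cannot show a change after it.

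**Ceiling on doses that a change could reach.** Already enrolled: 25 - 23 = 2. Still to come: 23 patients x 1 dose = 23 doses. Doses on POD 2 are unaffected, and doses withheld under the other criteria also drop out. The plan gives no distribution of dosing days and no expected hold rate, so the result is a range of 0 to 23 doses with no point estimate.

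**After the change.** With the marker drawn before the dose on days 2-4, its age is 0 days for a dose on POD 2, 3 or 4.

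**The case against.** The strongest reply is that the POD 2 column stands for the dosing visit. Table 1 has no POD 3 or 4 column even for vital signs and adverse events, yet the research nurse visits daily through POD 7 (Section XI.C) and vital signs are taken at the dose. RoTEM sits under POD 2 with a window of days 2-4, and the only postoperative research entry for the marker is in that column. On this view the gap is an incomplete footnote. That may well be so, and the time line figure that might settle it is not available in the text reviewed. But only RoTEM is given the wider window, so as written the marker is not. If that was the intent, the same small edit states it.

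The second reply is that other safeguards narrow the risk. This stands. Symptoms and EKG changes hold the dose on their own, EKG is marked as standard of care in every Table 1 column through POD 7, the POD 0-2 values give a trend, and nothing stops clinicians from ordering another marker.

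The third reply is that no rule is broken. This also stands: the documents set no maximum marker age.

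Four stronger readings are tempting, and the documents do not support them:

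- *The marker is research-only, so routine care would not fill the gap.* Section VIII says that "cardiac biomarkers, serum creatinine, thromboelastographic and liver transaminase measurements will be obtained specifically for research purposes", but its next sentence reads "Other tests conducted (e.g. hemoglobin concentration, creatinine, EKG) will be part of standard of care". Creatinine is in both lists, so the passage does not separate research tests from routine ones, and Table 1 marks troponin/CK-MB as S on POD 0 and POD 1. Only the blank cells after POD 2 set the marker apart.
- *Hemoglobin and EKG need a fixed recency window too.* Neither has a scheduled entry between POD 2 and POD 5, but Section VIII and Table 1 treat both as routine care. A 24-hour limit would be a reviewer's preference.
- *All 25 treated patients are exposed.* That count includes two already enrolled, and it ignores POD 2 doses, which are unaffected.
- *The adherence endpoint is undermined.* With no maximum marker age in the plan, a POD 4 dose that relies on a falling POD 2 trend complies with the rule as written.

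**Conclusion.** The concern holds as a minor safety point about timing. Under the written schedule, a POD 3 or POD 4 dose can rest on a troponin/CK-MB value 1 or 2 days old, whereas RoTEM is tied to the dose. The residual case needs four things together: a marker rise after POD 2, no symptoms, no EKG change and no clinician-ordered test. At most 23 future doses could be affected. The actual number is lower and cannot be derived from the documents.

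This rests on reading Table 1 literally, with the marker's POD 2 entry meaning POD 2. It also assumes that routine care does not reliably add a marker on POD 3 or 4, which the documents neither state nor rule out. The hold criteria and their thresholds are not in question.

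**What to change.** Keep the POD 2 marker, so that the trend point is not lost, and make two edits:

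1. Extend the RoTEM footnote in Table 1 to the marker row: *RoTEM EXTEM and troponin T/CK-MB to be obtained before the postoperative EPO dose, 2-4 days after surgery.*
2. Add troponin T/CK-MB to the draw listed under Post-Operative Dose in Section III, using a routine sample where one is available.

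The cost is at most one extra marker test per patient dosed on POD 3 or 4. A POD 2 dose needs none, provided that the POD 2 marker is drawn before the injection.

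One practical check is the limit in Section X of 8 mL of study blood per day, which does not count tests done as routine care. RoTEM takes about 3 mL, leaving 8 - 3 = 5 mL. The plan gives no separate volume for the marker, so the team should confirm that it fits whenever no routine sample can be used. The POD 2 column already pairs a research RoTEM with a marker that may be a research test, under the same limit.

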Anemic patients scheduled to undergo CABG, valve, or CABG/valve surgeries will be considered for the study. Patients who fulfill all the inclusion/exclusion criteria will be asked to participate in the study. The proportion of screen failures and eligible patients who refuse to participate will be recorded using a screen failure log. Patients who agree to be in the study and sign an informed consent form will be sequentially enrolled into the treatment group. The treatment group will receive up to three doses of EPO 300U/kg. The first dose of study medication will be administered up to 28 days before the day of surgery and the second will be administered 1-7 days before the day of surgery. These first two doses will be given at least 7 days apart. A third dose may be administered two to four days following surgery. All 3 doses will be administered subcutaneously and per surveillance strategy guidelines. In addition, supplementation

with IV iron (feraheme; 510mg delivered per IV infusion over a minimum of 15 minutes) will be given following the first two preoperative doses of EPO.

Differences in hemoglobin levels and reticulocyte counts from baseline to the day of surgery (preop to POD#0) and postoperative day five (POD#5), proportion of patients receiving erythrocyte transfusions and number of blood products (RBC, platelets and plasma) utilized and pre-defined clinical events (mortality, major cardiac, renal, neurological events [associated with anemia] and infection) will be assessed in all treated participants. Each patient will be enrolled in the study up to 28 days before the day of surgery and for up to 30 days following the day of surgery. This feasibility propensity-matched study will sequentially enroll 23 more treatment subjects to total 25. The propensity-matching control group will be comprised of 25 total “like” patients for comparison. The source of the data for the control group will be the Society of Thoracic Surgery (STS) Database, an institutional registry.

Study medications:

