The decision to initiate and continue administering doses of EPO is based on evidence accrued from randomized controlled trials and clinical practice guidelines provided by multiple sub-specialty and international societies.^{14,40-41} Substantial heterogeneity exists in factors that could be included in a surveillance strategy to minimize the risk of a thrombotic event in this setting; with no one strategy proven to be superior. The surveillance strategy included in this protocol derives from, what we believe to be, the most current safety analyses of perioperative EPO use reflected in the literature. Implementing such surveillance methods are intended to minimize the possibly rare but potentially life-threatening adverse events. Risk factors considered in our surveillance strategy include: evidence of unstable angina or myocardial infarction, recent thrombotic event, hemoglobin levels associated with a higher risk of a

myocardial event, excessive thrombocytosis (platelet count $>300 \times 10^3/\mu\text{L}$) or laboratory evidence of a hypercoagulable postoperative state.

EPO dosing will be stratified based on patient risk (degree of perioperative anemia), type of procedure (CABG vs. valve) and laboratory data (Hb, RoTEM: MCF) in the following manner:

Initial dosing/Re-dosing of EPO plus IV iron (Prior to Surgical Procedure):

Therapy or a dose will **NOT** be administered in patients under the following conditions:

- Patients scheduled for a CABG procedure with Hb concentration $\geq 12.5\text{g/dL}$
- Patients scheduled for a cardiac valve procedure with Hb concentrations $\geq 13.5\text{g/dL}$
- Rate of rise in Hb level that exceeds 1g/dL in past 7 days (and not secondary to erythrocyte transfusion)^a
- Evidence of any new or evolving symptoms or signs suggesting the presence of myocardial ischemia, including chest pain, EKG changes, or elevation of laboratory cardiac biochemical (CK-MB, Troponin)
- Average of three diastolic blood pressures (over 1hr) $>100\text{mmHg}$ despite scheduled anti-hypertensive therapy.

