Screening for Potential Participants: A HIPAA waiver was obtained to allow the research team to screen the medical records of patients scheduled for CABG, valve or CABG/valve surgery at UTSW University Hospital eligible for participation in this study. At the initial consultation with the cardiothoracic service or through Patient Blood Management Clinic, patients who fulfill the initial entry criteria for the study will be invited to participate in this propensity-matched study for patients with “low preoperative blood counts (or anemia)”. Patients who agree to be part of the study will be approached by members of the research team, who will explain the protocol in detail and will ask the patient to sign a written informed consent. Patients that become aware of the trial via the UT Southwestern clinical research website, will be referred directly to the clinical research nurse to answer all their questions and be encouraged to discuss possible participation with their surgeon during their next appointment.

Baseline Research Visit (7-28 days before day of surgery):

- Patients will be asked to sign the informed consent and HIPAA forms should they decide to proceed with the study.
- Patients will be escorted from the cardiothoracic surgery clinic by a member of the clinical research team or asked to come to the UTSW Patient Blood Management Clinic, Zale Lipshy University Hospital at [name]
- Data on demographics, vital signs, medical history, current medications, height, and weight will be recorded.
- We will review all available lab results.
- The patient will be enrolled into the treatment group.
- Treatment group patients will receive a single subcutaneous injection of EPO 300U/kg and an IV iron infusion of 510mg. Vital signs including heart rate, blood pressure, oxygen saturation, and temperature will be recorded before, during, and after drug administration.
- Patient will be monitored for any serious reactions during drug administration and for at least 30 minutes following each infusion. Serious reactions include anaphylaxis, chest pain, dyspnea, seizures, severe headache, fever, nausea, vomiting, and diarrhea, an increase in blood pressure greater than 20mmHg above baseline systolic, systolic BP greater than 180mmHg and/or diastolic BP greater than 100mmHg, hypotension.
- The visit will last approximately 1.5 hours.

Pre-op Visit (1-7 days before surgery)

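### Isolated-CABG patients with Hb 12.5 to 12.9 g/dL meet the entry criterion and join the treatment group, but the dosing rule withholds their first EPO and iron dose

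*Combined protocol and SAP*

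**What the plan says.** **Entry.** Section VI, criterion 2, reads: "The subject must be diagnosed with preoperative anemia, defined as hemoglobin <13.0g/dL". Criterion 3 admits CABG, valve and combined CABG/valve surgery, and the Hb limit does not vary by procedure. No exclusion in Section VII sets a lower ceiling for CABG.

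**Group.** Section III, Research Design and Methods: "Patients who agree to be in the study and sign an informed consent form will be sequentially enrolled into the treatment group". That group is to reach 25, with 23 still to be enrolled. The baseline visit list repeats the step: "The patient will be enrolled into the treatment group".

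**First dose.** The next item in that list is: "Treatment group patients will receive a single subcutaneous injection of EPO 300U/kg and an IV iron infusion of 510mg". It states no Hb condition. Research Design and Methods, however, makes every EPO dose conditional: "All 3 doses will be administered subcutaneously and per surveillance strategy guidelines".

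**Hold rule.** In the Surveillance Strategy for ESA Dosing, the preoperative heading begins "Initial dosing/Re-dosing of EPO plus IV iron (Prior to Surgical Procedure", so it names the initial dose and both drugs. Two of the conditions under which treatment is not given are:

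- "Patients scheduled for a CABG procedure with Hb concentration" of 12.5 g/dL or more;
- "Patients scheduled for a cardiac valve procedure with Hb concentrations" of 13.5 g/dL or more.

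**The concern.** The entry limit and the first-dose limit are in the wrong order for CABG. For valve surgery the hold lies above the entry limit, so it acts only once Hb has risen, as one would expect of a safety stop. For CABG it lies below the entry limit, so it can act on the day of enrolment. The rationales given in the surveillance section concern the rate of Hb rise and postoperative Hb. Neither explains why a CABG patient should be admitted for treatment at a level where treatment is barred.

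Three things are at stake. Aim 1 is the proportion who are eligible and agree, and it counts patients whom the dosing rule will not let start. The treatment group is small, and some of its places may go to patients with no preoperative treatment. Section III also says that means and standard deviations for Hb, reticulocytes and transfusion may feed the RCT sample size. If undosed patients are analysed as treated, those figures describe a mixture.

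**Working it through.** The plan gives no figure to reproduce here, and the Biostatistics section says that no formal power calculation was done. The check compares two intervals and then follows one patient through the text.

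**1. Intervals**

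| Procedure | Entry (Section VI) | First dose withheld (Section III) | Entry limit minus hold limit | Overlap |
|---|---|---|---|---|
| CABG | Hb <13.0 | Hb ≥12.5 | 13.0 − 12.5 = +0.5 g/dL | 12.5 to 12.9 (five values at one decimal) |
| Valve | Hb <13.0 | Hb ≥13.5 | 13.0 − 13.5 = −0.5 g/dL | none |
| CABG/valve | Hb <13.0 | limit not named | cannot be computed | unknown |

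**2. One patient, isolated CABG, Hb 12.7 g/dL**

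- Criterion 2 is met, since 12.7 < 13.0.
- After consent the patient is placed in the treatment group.
- The first dose is barred, since 12.7 ≥ 12.5.
- Table 1 puts the eligibility check and a CBC in the same 7-28 day preoperative column, so one Hb value can both admit the patient and stop the dose.

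Two phrases in Section IX might have removed this patient. The surgeon's judgement of suitability carries no Hb limit. The wording on giving the first dose when appropriate concerns whether it is given at the consent visit or at a later appointment.

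**3. Size per patient**

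- Share of the treatment group: 1/25 = 4.0%.
- Already enrolled: 25 − 23 = 2. Share of the remaining places: 1/23 = 4.3%.

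**4. Aim 1.** Let N patients be screened, E be eligible as written, and B of those lie in the CABG band. The plan reports E/N. The proportion who could start treatment, as far as this Hb hold is concerned, is (E − B)/N. The overstatement is B/N. The documents give no Hb distribution and no CABG share, so B is unknown.

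**5. Dilution, as an illustration only.** Assume that k of the 25 are undosed, that their Hb changes like that of controls, that they are analysed as treated, and that the SD is unchanged. With f = k/25, the mean effect is multiplied by (1 − f), and a sample size based on it by 1/(1 − f)².

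| k (assumed) | f | Effect retained | RCT size factor |
|---|---|---|---|
| 0 | 0 | 1.00 | 1.00 |
| 1 | 0.04 | 0.96 | 1/0.9216 = 1.09 |
| 5 | 0.20 | 0.80 | 1/0.64 = 1.56 |

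The range of k is an assumption. Nothing in the documents makes any value of it more likely than another.

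**The case against.** The best defence is that eligibility and dosing are separate layers by design. The surveillance section governs both starting and continuing EPO, the plan promises at most three doses, and all of them are subject to that strategy. On this reading a held first dose is foreseen, and the unconditional baseline item is not a competing rule. The last part stands: the texts can be reconciled, and a reader should not infer that the protocol orders a dose which its safety rule forbids.

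The rest explains how a held patient arises, but not why one should be enrolled for treatment at an Hb already above the dosing limit. Ischemia and diastolic pressure can also stop a first dose, but those holds overlap in part with exclusions 1 and 3. The CABG Hb hold has no counterpart among the entry criteria.

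Several limiting points stand in full:

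- Adherence counts only doses that the surveillance strategy allows, so a correctly held dose is not a failure. One might infer that the adherence criterion is compromised; the Clinical Outcomes section does not support that.
- The hold is not permanent. Hb may fall below 12.5 g/dL before a later visit, and the postoperative dose has its own limit (withheld above 10.0 g/dL). One cannot infer that these patients are never treated.
- The analysis is mainly descriptive, and tests are to be read with caution.
- Section III speaks of assessing those treated, which can be read as leaving out undosed patients. Dilution is then avoided, but fewer than 25 treated patients remain. The timeline and CONSORT diagrams are not visible in the text reviewed and may show how held patients are handled.
- If the RCT kept the same entry and hold rules and analysed everyone enrolled, a diluted estimate would be the relevant planning value. The plan does not say that this is intended.

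It can also be argued that one sentence on how held patients are counted would do, without touching eligibility. That would settle the analysis, but it would not free the places or correct the reading of Aim 1.

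**Conclusion.** The conflict holds for isolated CABG between 12.5 and 12.9 g/dL and follows from the text alone. As written, the plan counts these patients as eligible, gives them treatment places, and withholds their first EPO and iron dose for as long as Hb stays at or above 12.5 g/dL.

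The size is 4.0% of the treatment group per patient, times an unknown number of patients. A reader might infer that a material share of the 25 will go untreated; the documents give no basis for any particular share. The effect on Aim 1 needs only that some such patients are screened and found eligible. The effect on the Hb and transfusion estimates needs, in addition, that they are analysed as treated.

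The same conclusion should not be extended to combined CABG/valve surgery, for which no hold limit is named, nor to valve surgery, where there is no overlap at entry.

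**What to change.** For patients still to be enrolled:

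1. Set the CABG entry limit at Hb below 12.5 g/dL. Equivalently, require that the surveillance strategy's Hb hold is not met at baseline.
2. Apply the same limit when selecting controls from the STS registry, so that both groups come from the same Hb range.
3. For Aim 1, report the eligible proportion under both limits, with the number of CABG patients at 12.5 to 12.9 g/dL, and state whether either of the two patients already enrolled was in that band. The screen failure log can supply the count if it records whether the other criteria were met.

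The cost is amendment wording, a slightly smaller eligible pool, and a mid-study change of entry that splits the Aim 1 count. Agreement to take part will not be observed for band patients who are no longer approached, so after the change only eligibility can be given under the wider limit.

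Two wording points are optional and not part of this finding: naming the Hb limit for combined CABG/valve surgery, and saying what happens when the first dose falls on day −7, which leaves no preoperative day for a second dose at least 7 days later.
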